## 6.7 Multiplicity

No multiplicity adjustment needs to be considered for the effectiveness endpoints since no formal hypothesis testing will be conducted.

## 6.8 Safety Analysis

The safety endpoints for this study are AEs, biomicroscopy findings, and device deficiencies.

Descriptive summaries (counts and percentages) for ocular and nonocular AEs will be presented by Medical Dictionary for Regulatory Activities Preferred Terms. AEs leading to study discontinuation, significant non-serious AEs, and SAEs will be identified. Individual subject listings will be provided, as necessary.

Individual subject listings will be provided for AEs that occur after signing informed consent but prior to exposure to study lenses.

Each biomicroscopy parameter will be tabulated by its grade. For each biomicroscopy parameter, counts and percentages of eyes that experience an increase of  $\geq 2$  grades from baseline (Visit 1) to any subsequent visit will be presented. A supportive listing will be generated which will include all biomicroscopy data from all visits in the corresponding period for these eyes experiencing the increase.

Two listings (prior to exposure of study lenses and treatment-emergent) of device deficiencies, as recorded on the Device Deficiency Form, will be provided. Additionally, each device deficiency category will be tabulated.

No inferential testing will be done for safety analysis.

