**Table 1-1 Schedule of Study Procedures and Assessments**

Procedure/ Assessment	Visit 1 Screen / Baseline/ Lens 1: Dispense [Day 1]	Visit 2 Lens 1: Week 1 Follow-up [Day 8 (± 2 days)] §	Visit 3 Lens 1: Month 1 Follow-up [Day 30 (± 2 days)] Lens 2: Dispense [Day 1]		Visit 4 Lens 2: Week 1 Follow-up [Day 8 (± 2 days)] §	Visit 5 Lens 2: Month 1 Follow-up/ Exit^ [Day 30 (± 2 days)] §	Unscheduled Visit
			Follow-up Lens 1 §	Dispense Lens 2			
Informed Consent	X						
Demographics	X						
Medical History	X	X	X	X	X	X	X
Concomitant Medications	X	X	X	X	X	X	X
Inclusion/ Exclusion	X						
Habitual lens (brand, power*, care)	X						
VA w/ habitual correction* (OD, OS, logMAR distance)	X					X	(X)
████████████████████	█		█			█	
Manifest refraction*	X	(X)	(X)	(X)	(X)	(X)	(X)
BCVA* (OD, OS, logMAR distance with manifest refraction)	X	(X)	(X)	(X)	(X)	(X)	(X)
Biomicroscopy	X	X	X		X	X	X
████████████████████	█	█	█	█	█	█	█
Randomization	X						
Dispense study lenses	X			X			(X)
VA w/ study lenses, (OD, OS, logMAR distance)	X	X	X	X	X	X	(X)
████████████████████	█	█	█	█	█	█	█
████████████████████	█	█	█	█	█	█	█

Printed By:

Print Date:

Procedure/ Assessment	Visit 1 Screen / Baseline/ Lens 1: Dispense [Day 1]	Visit 2 Lens 1: Week 1 Follow-up [Day 8 (± 2 days)] §	Visit 3 Lens 1: Month 1 Follow-up [Day 30 (± 2 days)] Lens 2: Dispense [Day 1]		Visit 4 Lens 2: Week 1 Follow-up [Day 8 (± 2 days)] §	Visit 5 Lens 2: Month 1 Follow-up/ Exit^ [Day 30 (± 2 days)] §	Unscheduled Visit
			Follow-up Lens 1 §	Dispense Lens 2			
[REDACTED]	[REDACTED]	[REDACTED]	[REDACTED]	[REDACTED]	[REDACTED]	[REDACTED]	[REDACTED]
[REDACTED]	[REDACTED]	[REDACTED]	[REDACTED]	[REDACTED]	[REDACTED]	[REDACTED]	[REDACTED]
[REDACTED]	[REDACTED]	[REDACTED]	[REDACTED]	[REDACTED]	[REDACTED]	[REDACTED]	[REDACTED]
[REDACTED]	[REDACTED]	[REDACTED]	[REDACTED]	[REDACTED]	[REDACTED]	[REDACTED]	[REDACTED]
[REDACTED]	[REDACTED]	[REDACTED]	[REDACTED]	[REDACTED]	[REDACTED]	[REDACTED]	[REDACTED]
[REDACTED]	[REDACTED]	[REDACTED]	[REDACTED]	[REDACTED]	[REDACTED]	[REDACTED]	[REDACTED]
[REDACTED]	[REDACTED]	[REDACTED]	[REDACTED]	[REDACTED]	[REDACTED]	[REDACTED]	[REDACTED]
[REDACTED]	[REDACTED]	[REDACTED]	[REDACTED]	[REDACTED]	[REDACTED]	[REDACTED]	[REDACTED]
AEs	X	X	X	X	X	X	X
Device deficiencies	X	X	X	X	X	X	X
Exit Form	(X)	(X)	(X)	(X)	(X)	X	(X)

\* Source only

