### 5.1.3 Visit 3 (Day $30 \pm 2$ Days) – Lens 1: Month 1 Follow-up. Lens 2: Dispense

1.	Obtain information on any changes in medical health and/or the use of concomitant medications.
2.	Record any device deficiencies or AEs, including those associated with changes in concomitant medication dosing, which are observed or reported since the previous visit(s).
	[REDACTED]
	[REDACTED]
	Confirm the subject has worn the study lenses for a minimum of 6 hours on the day of follow-up visit.
	[REDACTED]
5.	Evaluate the study lenses by performing the following: 

• logMAR VA with study lenses (OD and OS, at distance)

	
[REDACTED]
 
[REDACTED]
 
[REDACTED]
 
[REDACTED]
 
[REDACTED]
 
[REDACTED]
 
[REDACTED]

	
[REDACTED]
 
[REDACTED]
 
[REDACTED]

	
[REDACTED]

9.	
Perform slit-lamp biomicroscopy (without contact lenses) to evaluate the following:
 
 
• Limbal hyperemia
 
• Bulbar hyperemia
 
• Corneal staining
 
• Conjunctival staining
 
• Palpebral conjunctival observations
 
• Corneal epithelial edema
 
• Corneal stromal edema
 
• Corneal vascularization
 
• Conjunctival compression/indentation
 
• Chemosis
 
• Corneal infiltrates
 
• Other findings
 

10.	
Based upon the randomized treatment sequence, have the subject insert the appropriate study Lens 2, being careful to maintain the correct OD and OS lens assignments [REDACTED]
 
[REDACTED]
 
 
• Keep all lidding foils of lenses used during lens fit process for study lens accountability.
 
• Follow procedures to maintain masking.
 

11.	
Evaluate the study lenses by performing the following:
 
 
• logMAR VA with study lenses (OD and OS, at distance)*
 
 
*VA w/study lenses must be 20/25 in each eye or better for subject to leave the office

13.	Dispense study lenses, new lens case, and lens care solution. Provide the subject with written and verbal instructions on lens wear and care.

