## **2 Analysis Sets**

### **2.1 Safety Analysis Set**

Safety analyses will be conducted using the safety analysis set on a treatment-emergent basis. As such, the safety analysis set will include all subjects/eyes exposed to any study lenses evaluated in this study. For treatment-emergent safety analyses, subjects/eyes will be categorized under the actual study lenses exposed in the corresponding lens sequence.

Adverse events occurring from the time of informed consent but prior to first exposure to study lenses will be summarized in subject listings.

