### **5.3 Statistical Methods for Safety Analyses**

The analysis set for all safety analyses is defined in Section 2.1. Baseline will be defined as the last measurement prior to exposure to study lenses (ie, Visit 1). Safety variables will be summarized descriptively.

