#### **5.3.1 Adverse Events**

The applicable definition of an AE is in the study protocol. All AEs occurring from when a subject signs informed consent to when a subject exits the study will be accounted for in the reporting.

Pre-treatment AEs will be separated from treatment-emergent AEs occurring during the study period. A pre-treatment AE is an event that occurs after signing informed consent but prior to exposure to study lenses. The period for treatment-emergent AE analysis starts from exposure to study lenses until the subject completes or is discontinued from the study. Each AE will be summarized under the exposed lens based upon the event onset date/time, up until the start of the next lens in the crossover sequence.

The following tables and supportive listings will be provided:

- Incidence of All Ocular Treatment-Emergent Adverse Events
- Incidence of All Nonocular Treatment-Emergent Adverse Events
- Listing of All Ocular Treatment-Emergent Adverse Events
- Listing of All Nonocular Treatment-Emergent Adverse Events
- Listing of All Ocular Pre-Treatment Adverse Events
- Listing of All Nonocular Pre-Treatment Adverse Events

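### Biomicroscopy rises of two or more grades are measured from Visit 1 in both periods, so a by-lens table also counts rises that persist from Lens 1 under Lens 2, and no planned count separates them

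*Protocol*

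**What the plan says.** The two documents agree on the reference visit. Protocol 6.8 says that the number and share of eyes rising by two or more "grades from baseline (Visit 1) to any subsequent visit will be presented". SAP 5.3 says, for safety variables generally, "Baseline will be defined as the last measurement prior to exposure to study lenses (ie, Visit 1"). Neither defines a second baseline for the second crossover period.

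The order of events at Visit 3 is in Protocol 5.1.3. Step 9 reads "Perform slit-lamp biomicroscopy (without contact lenses) to evaluate the following" and step 10 is to "have the subject insert the appropriate study Lens 2". The exam therefore comes just before first exposure to Lens 2, and no washout is described. Table 1-1 marks this exam in the Lens 1 follow-up column and leaves the biomicroscopy cell under "Dispense Lens 2" empty.

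For treatment-emergent safety analyses, SAP 2.1 says "subjects/eyes will be categorized under the actual study lenses exposed in the corresponding lens sequence". SAP 5.3.2 plans two biomicroscopy tables: grade frequencies by visit, and the incidence of rises of two or more grades. It adds listings of one-grade rises, of rises of two or more grades, of infiltrates and of other findings. For eyes with the larger rise, Protocol 6.8 says "A supportive listing will be generated which will include all biomicroscopy data from all visits in the corresponding period for these eyes"; the SAP restricts the one-grade and two-grade listings to relevant visits of the crossover period.

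Adverse events have their own rule in SAP 5.3.1: "Each AE will be summarized under the exposed lens based upon the event onset date/time", until the next lens starts. Biomicroscopy grades have no such rule.

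**The concern.** In a crossover without washout, an eye can enter the second period already changed. With Visit 1 as the only reference, a rise that began on the first lens and is still present a week or a month later meets the definition again under the second lens. A count labelled with the second lens then mixes two kinds of eye: those that changed while wearing it, and those already raised when it went in.

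Biomicroscopy is one of three safety endpoints, and the trial exists to describe how the test lens performs. A reader of the by-lens incidence table would want to know how many flagged eyes were already raised at the switch. The grade needed to answer that is collected at Visit 3, but no planned within-eye count uses it.

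**Working it through.** The plan states no expected rate of biomicroscopy change, so there is no figure to reproduce. The check is a logical one, followed by an illustration of size. Grades are assumed to start at 0; the exclusion criteria name only Grade 2 as mild and Grade 3 as moderate.

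**1. Which eyes are counted under Lens 2.** An eye is flagged if its highest grade at Visits 4 and 5, minus its Visit 1 grade, is at least 2. The Visit 2 grade is taken to be no higher than the Visit 3 grade.

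| Grades at Visits 1, 3, 4, 5 | Visit 3 minus Visit 1 | Lens 2 maximum minus Visit 1 | Counted under |
|---|---|---|---|
| 0, 2, 2, 2 | 2 | 2 | both lenses |
| 0, 1, 2, 2 | 1 | 2 | Lens 2 only |
| 0, 0, 2, 2 | 0 | 2 | Lens 2 only |

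All three score the same under Lens 2, although their status at the switch differs.

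**2. Whether any planned count separates them.** Take two eyes in the same sequence, with grades at Visits 1 to 5.

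- Set A: 0,0,2,2,2 and 0,0,0,0,0
- Set B: 0,0,2,0,0 and 0,0,0,2,2

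In both sets the frequencies are two eyes at Grade 0 at Visits 1 and 2, and one eye at each of Grades 0 and 2 at Visits 3, 4 and 5. In both sets one eye is flagged under Lens 1 and one under Lens 2. Yet the Lens 2 eye was already raised at Visit 3 in set A and newly raised in set B. The two planned tables are identical for both sets, so they cannot tell these cases apart.

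**3. Illustrative size.** From the documents: 32 completers, so 32 × 2 = 64 eyes, and 1:1 allocation to sequence. Assumed: lens X raises a share p_X of eyes by two or more grades and lens Y a share p_Y; reactions are independent; a share q of first-period rises is still present at a second-period visit, whichever lens came first.

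Eyes counted on X only through persistence = 64 × (1 − p_X) × 0.5 × p_Y × q.

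| p_X, p_Y | q = 0 | q = 0.5 | q = 1 |
|---|---|---|---|
| 2%, 2% | 0 | 0.31 | 0.63 |
| 5%, 5% | 0 | 0.76 | 1.52 |
| 10%, 10% | 0 | 1.44 | 2.88 |
| 0%, 10% | 0 | 1.60 | 3.20 |

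For example, 64 × 0.95 × 0.5 × 0.05 × 0.5 = 0.76, and 64 × 1 × 0.5 × 0.10 × 1 = 3.2.

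**4. Effect on the contrast between lenses.** The displayed rate on X is p_X + 0.5 × q × (1 − p_X) × p_Y, and likewise for Y. Subtracting gives (p_X − p_Y) × (1 − q/2). A true gap of 5% against 2% displays as 3 × 0.75 = 2.25 points at q = 0.5 and 3 × 0.5 = 1.5 points at q = 1. A true gap of 10% against 0% displays as 7.5 and 5 points.

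**5. Cell sizes if the Period 2 count is split.** At 5% on both lenses and q = 0.5, with every first-period rise taken as present at Visit 3, each lens has 32 eyes in Period 2. Flagged and not raised at Visit 3: 32 × 0.95 × 0.05 = 1.52. Flagged and already up two or more grades: 32 × 0.05 × (0.05 + 0.95 × 0.5) = 0.84, of which 32 × 0.05 × 0.05 = 0.08 react to both lenses.

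**The case against.** The strongest reply is that nothing here is an error. Visit 1 is the only exam before any study lens, it is a defensible reference, and protocol and SAP agree on it. That stands, and the Visit 1 table should stay.

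The title of the incidence table does not say it is by lens. A single overall count per eye would raise no attribution question. SAP 2.1 makes by lens the natural reading, and the unstated columns are only missing detail.

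The information is largely planned already. An eye raised at Visit 3 should appear in the Lens 1 listing of one-grade or larger rises, and the infiltrates listing is not confined to symptomatic cases. A reader might infer that persisting rises are hidden; they are not. What remains is that the separation needs hand-matching across periods and yields no reported count.

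A reader might also infer from Table 1-1 that the Period 2 listings leave out the Visit 3 grade. The documents do not say so. Visit 3 is also Day 1 of Lens 2, and the SAP wording on relevant visits can include it. Stating it would remove the doubt.

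Nor is the onset rule for adverse events an inconsistency: an event has an onset, whereas a grade is a status at a visit. Adverse event reporting covers part of the ground. Protocol 7.1 makes neovascularization of Grade 2 or more, corneal staining of Grade 3 or more, and symptomatic infiltrative events reportable. The other 8 of the 11 named parameters (11 less staining, vascularization and infiltrates) have no trigger of that kind in its list of significant non-serious events and depend on investigator judgement under Protocol 7.2. Those tables count events, not grade changes.

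Finally, the split cannot settle causation and its cells are small. Both are true and belong beside the table.

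**Conclusion.** The point holds as a minor reporting improvement. With Visit 1 as the only reference and no washout, a by-lens incidence table places rises that persisted from Lens 1 under Lens 2 as well, and no planned count separates them from rises that arose on Lens 2.

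Its size is unknown, because the documents give neither rates nor persistence. The range of 0 to 3.2 of 64 eyes per lens is illustrative only: its upper end follows from the assumed 10% cap, and it also rests on 32 completers, independence, equal persistence after either lens and a scale starting at 0.

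A reader might infer that the table would point to the wrong lens. The documents do not support that. Under equal persistence the displayed gap shrinks by the factor 1 − q/2 and keeps its sign; unequal persistence was not modelled, and the documents offer nothing to judge it by. The trial has no safety hypothesis, no inferential safety testing and no success criterion, so no error rate or decision is affected.

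**What to change.** In SAP 5.3.2:

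- Keep the Visit 1-referenced incidence table as primary.
- For each lens, split the Period 2 count by the eye's status at the Visit 3 pre-insertion exam relative to Visit 1: not raised, raised one grade, raised two or more grades. Report counts.
- State that the Period 2 listings show the Visit 1 and Visit 3 grades of each listed eye.

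A count referenced to Visit 3 should not replace the Visit 1 table. It would miss a sustained finding such as 0,2,2,2, and would flag 2,1,3,3, which is only one grade above Visit 1.

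The cost is a little programming and an SAP revision, or a note in the study report, which Protocol section 6 allows for departures from the plan. No new data are needed. Three limits should be stated with the table. The split cannot tell simple persistence from Lens 2 sustaining the finding, and eyes reacting to both lenses fall in the already-raised group. A rise seen at Visit 2 but resolved by Visit 3 is classed as not raised. The cells will be small.

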## 6.9 Interim Analyses

There are no plans to conduct an interim analysis and no criteria by which the study would be terminated early based upon statistical determination.

## 6.10 Sample Size Justification

## 7 ADVERSE EVENTS AND DEVICE DEFICIENCIES

### Terms and Definitions

Adverse Event (AE)	Any untoward medical occurrence, unintended disease or injury, or untoward clinical signs (including abnormal laboratory findings) in subjects, users or other persons, whether or not related to the investigational medical device (test product). Note: For subjects, this definition includes events related to the test product, the control product, or the procedures involved. For users or other persons, this definition is restricted to events related to the test product.
Adverse Device Effect (ADE)	AE related to the use of an investigational medical device (test product) or control product. Note: This definition includes AEs resulting from insufficient or inadequate instructions for use, deployment, implantation, installation, or operation; any malfunction; and use error or intentional misuse of the test product or control product.
Anticipated Serious Adverse Device Effect (ASADE)	Serious ADE which by its nature, incidence, severity or outcome has been identified in the risk management file.
Device Deficiency	Inadequacy of a medical device with respect to its identity, quality, durability, reliability, safety, or performance. Note: This definition includes malfunctions, use errors, and inadequate labeling.
Malfunction	Failure of a medical device to meet its performance specifications or otherwise perform as intended. Performance specifications include all claims made in the labeling of the device. The intended

	performance of the device refers to the intended use for which the device is labeled or marketed.
Non-serious Adverse Event	AE that does not meet the criteria for an SAE.
Serious Adverse Event (SAE)	
AE that led to any of the following:
 
 
• Death.
 
• A serious deterioration in the health of the subject that either resulted in: 
 
a) a life-threatening illness or injury. Note: Life-threatening means that the individual was at immediate risk of death from the event as it occurred, ie, it does not include an event which hypothetically might have caused death had it occurred in a more severe form.
 
b) any potentially sight-threatening event or permanent impairment to a body structure or a body function.
 
c) in-patient hospitalization or prolonged hospitalization. Note: Planned hospitalization for a pre-existing condition, without serious deterioration in health, is not considered an SAE. In general, hospitalization signifies that the individual remained at the hospital or emergency ward for observation and/or treatment (usually involving an overnight stay) that would not have been appropriate in the physician's office or an out-patient setting. Complications that occur during hospitalization are adverse events. If a complication prolongs hospitalization or fulfills any other serious criteria, the event is serious. When in doubt as to whether "hospitalization" occurred, the event should be considered serious.
 
d) a medical or surgical intervention to prevent a) or b).
 
e) any indirect harm as a consequence of incorrect diagnostic test results when used within manufacturer's instructions for use.
 
 
 
• Fetal distress, fetal death, or a congenital abnormality or birth defect.
 
 
Refer to Section 7.1 for additional SAEs.

Serious Adverse Device Effect (SADE)	ADE that has resulted in any of the consequences characteristic of an SAE.
Significant Non-Serious Adverse Event	A significant non-serious AE is a symptomatic, device-related, non-sight threatening AE that warrants discontinuation of any contact lens wear for greater than or equal to 2 weeks. Refer to Section 7.1 for additional Significant Non-Serious AEs.
Unanticipated Serious Adverse Device Effect (USADE)	Serious adverse device effect which by its nature, incidence, severity or outcome has not been identified in the risk management file.
Use Error	Act or omission of an act that results in a different medical device response than intended by manufacturer or expected by user. Note: This definition includes slips, lapses, and mistakes. An unexpected physiological response of the subject does not in itself constitute a use error.

### 7.1 General Information

An AE is any untoward medical occurrence, unintended disease or injury, or untoward clinical signs (including abnormal laboratory findings) in subjects, users, or other persons, whether or not related to the investigational medical device (test *product*).

Figure 7-1 Categorization of All AEs

[figure not shown]
[figure not shown]

Figure 7-2

## Categorization of All Serious Adverse Events

**Specific Events Relevant to this Protocol*****Serious Adverse Events***

In addition to reporting all AEs (serious and non-serious) meeting the definitions, the Investigator must report any occurrence of the following as an SAE:

- An ocular infection including a presumed infectious ulcer with any of the following characteristics:
  - Central or paracentral location
  - Penetration of Bowman's membrane
  - Infiltrates > 2 mm diameter
  - Iritis
  - Increase in intraocular pressure
  - Culture positive for microorganisms
  - Increasing size or severity at subsequent visits
- Any central or paracentral corneal event (such as neovascularization) that results in permanent opacification
- Hypopyon

- Hyphema
- Neovascularization within the central 6 mm of the cornea
- Permanent vision loss as defined by loss of 2 or more lines of BCVA from enrollment visit that fails to resolve
- Uveitis (anterior, intermediate, or posterior)
- Corneal abrasion affecting  $\geq 50\%$  of corneal surface area

### ***Significant Non-Serious Adverse Events***

A significant non-serious AE is a symptomatic, device-related, non-sight threatening AE that warrants discontinuation of any contact lens wear for greater than or equal to 2 weeks. In addition, the Investigator must report any occurrence of the following as a Significant Non-Serious AE:

- Peripheral non-progressive non-infectious ulcers
- All symptomatic corneal infiltrative events
- Corneal staining score greater than or equal to Grade 3
- Temporary vision loss as defined by loss of 2 or more lines of BCVA from enrollment visit that persists for 2 or more weeks
- Neovascularization score greater than or equal to Grade 2

*The above events are based upon the categories provided in the ISO 11980 and the US FDA Premarket Notification (510(k)) Guidance Document for Daily Wear Contact Lenses and Contact Lens Care Products.*

### ***Device Deficiencies***

A device deficiency is inadequacy of a medical device with respect to its identity, quality, durability, reliability, safety, or performance. A device deficiency may or may not be associated with patient harm (ie, ADE or SADE); however, not all ADEs or SADEs are due to a device deficiency. The Investigator should determine the applicable category listed in the Device Deficiency eCRF for the identified or suspect device deficiency and report any patient harm separately. Examples of device deficiencies include the following:

- Failure to meet product specifications (eg, incorrect lens power/diameter/base curve/color)

- Lens/solution cloudy
- Lens surface/edge defect
- Torn lens during handling/in pack
- Packaging deficit (eg, mislabeled product, tampered seal, leaking bottle/container)
- Suspect product contamination
- Lack of performance

